### Hyperglycemia

- Blood glucose self-monitoring

The Principal Investigator will educate the patient on the signs and symptoms of hyperglycemia. Patients must monitor their fasting blood glucose by finger stick at home at least 3 times per week for the first 4-week treatment with pasireotide or when the dose of pasireotide is increased. If a patient does not have any fasting values above 100mg/dL, monitoring can be decreased to at least 2 times per week from week 4 to week 12 and 1 time every week for the rest of the study. If any values are observed above 100mg/dL, the guidelines based on the current recommendations from the 2012 ADA aiming at a glycemic treatment goal of FPG < 130mg/dL (<7.2mmol/L) will be followed. Appropriate actions such as initiation of anti-hyperglycemic therapy (and referral to diabetes specialist) will be taken by the investigator.

Patients will be required to keep a diary for their blood glucose for appropriate management throughout the study and present the collected data to the principal investigator for evaluation.

Close and frequent monitoring of blood glucose is needed during pasireotide treatment. Intervention for hyperglycemia will be implemented by the Subject's endocrinologist in conjunction with the Sponsor-Investigator as per standard clinical practice in any patient meeting any of the following criteria: FPG > 130mg/dL or HbA1c  $\geq$  6.5%.

Patients with FPG > 160mg/dL or HbA1c > 7.5% despite adjustment of antidiabetic therapy may also be referred to a diabetes specialist (or earlier per investigator's judgment).

Patients with grade 3 hyperglycaemia (FPG value > 250mg/dL; >13.9 mmol/L) at any point in the study will have the dose of pasireotide decreased. Patients who in spite of appropriate therapeutic interventions and despite dose reduction of study drug develop uncontrolled diabetes mellitus and/or consistently high blood glucose values: FPG  $\geq$  240mg/dL (13.3 mmol/L) or HbA1c value  $\geq$  10% will require study treatment discontinuation.

### 3.4.3 Serious adverse events

Information about all serious adverse events will be collected and recorded on study-specific Serious Adverse Event Report source documents. To ensure patient safety each serious adverse event will be reported as described below. A serious adverse event is an undesirable sign, symptom, or medical condition which:

1. is fatal or life-threatening
2. required or prolonged hospitalization
3. results in persistent or significant disability/incapacity
4. constitutes a congenital anomaly or a birth defect
5. are medically significant, may jeopardize the subject and may require medical or surgical intervention to prevent one of the outcomes listed above.

Events **not** considered to be serious adverse events are hospitalizations for the:

- routine treatment or monitoring of the studied indication, not associated with any deterioration in condition
- treatment, which was elective or pre-planned, for a pre-existing condition that did not worsen
- treatment on an emergency, outpatient basis for an event **not** fulfilling any of the definitions of serious given above and **not** resulting in hospital admission.

Pregnancy, although not itself a serious adverse event, will also be reported on a serious adverse event form (as described below) and be followed up to determine outcome, including spontaneous or voluntary termination, details of birth, and the presence or absence of any birth defects or congenital abnormalities.

#### 3.4.4 Adverse Event Review and Reporting

To ensure patient safety, every adverse event, regardless of relationship to the drug and occurring after the patient has provided informed consent until at least 8 weeks after the patient has stopped study drug administration, will be reviewed by the Sponsor -Investigator. Any event that meets the definition of an Unanticipated Problem (UP) as per the CUMC IRB's UP Policy will be reported promptly, but no later than a week following the occurrence of the event or the PI's knowledge of the event. All adverse events will be reviewed by the Sponsor-Investigator at the time of learning of the adverse event from the study subject, on receipt of a laboratory value or any other source for determination of seriousness and need for actions as described above. All events will be recorded in the subject charts and an Adverse Event log. All SAEs will be reported Novartis per the following specific reporting requirements.

##### Reporting of SAEs to the drug manufacturer/supplier:

The Sponsor-Investigator will notify the drug manufacturer, Novartis, of all Serious Adverse Events irrespective of causality, encountered in the Clinical Trial **within twenty-four (24) hours of becoming aware of it**. Each such notice will be reported to Novartis on a MedWatch form (<http://www.fda.gov/downloads/AboutFDA/ReportsManualsForms/Forms/UCM163919.pdf>) and transmitted to Novartis via fax utilizing a Novartis provided fax cover sheet (Appendix 7.4, Exhibit A). All information about all SAEs will be collected and recorded on this form; all applicable sections of the form will be completed in order to provide a clinically thorough report. The investigator will assess and record the relationship of each SAE to the study treatment. The fax confirmation sheet will be kept with the source documents at the study site.

To ensure patient safety every SAE regardless of suspected occurring after the patient has provided informed consent and until at least 8 weeks (for LAR) or 30 days (s.c.) after the patient has stopped study drug administration will be reported. Any SAEs experienced after this 8 weeks (LAR) or 30 days (s.c.) period should only be reported to Novartis if the investigator suspects a causal relationship to the study treatment. Recurrent episodes, complications, or progression of the initial SAE must be reported as follow-up to the original episode within 24 hours of the investigator receiving the follow-up information. An SAE occurring at a different time interval or otherwise considered completely unrelated to a previously reported one will be reported separately as a new event. Follow-up information is sent to the same contact(s) to whom the original SAE Report Form was sent, using a new MedWatch Form stating that this is a follow-up to the previously reported SAE and giving the date of the original report. Each re-occurrence, complication, or progression of the original event will be reported as a follow-up to that event regardless of when it occurs. The follow-up information will describe whether the event has resolved or continues, if and how it was treated, whether the blind was broken or not, and whether the patient continued or withdrew from study participation.

If the SAE is not previously documented in the current Investigator's Brochure or Package Insert (new occurrence) and is thought to be related to the Novartis study treatment, an oncology Novartis Drug Safety and Epidemiology (DS&E) department associate may urgently require further information from the investigator for Health Authority reporting. Novartis may need to issue an Investigator Notification

(IN), to inform all investigators involved in any study with the same drug that this SAE has been reported. Suspected Unexpected Serious Adverse Reactions (SUSARs) will be collected and reported to the competent authorities and relevant ethics committees in accordance with Directive 2001/20/EC or as per national regulatory requirements in participating countries.

### **Reporting of Unanticipated Problems (UP)**

**A UP** is any incident, experience or outcome involving risk to subjects or others in any human subjects research that meets all of the following criteria:

- Unexpected (in terms of nature, severity or frequency) given (a) the research procedures that are described in the IRB-approval protocol and informed consent document and (b) the characteristics of the subject population being studied;
- Related or possibly related to participation in such research (i.e., there is a reasonable possibility that the incident, experience or outcome may have been caused by the procedures involved in such research); and
- Suggests that the research places subjects or others at a greater risk of harm (including physical, psychological, economic or social harm) than was previously known or recognized (HHS IRB Guidance, Section I).

#### **At the time of the Occurrence of an Unanticipated Problem:**

Each UP will be reported to the IRB, whether or not (a) it is serious or non-serious.

The UP will be reported promptly, but not later than one week following the occurrence of the UP or the PI's acquiring knowledge of the UP.

The Principal Investigator will make the determination as to whether an incident, experience or outcome constitutes a UP.

Each UP will be reported to the IRB using the Unanticipated Problem Report module in Rascal.

The investigator will conclude in the Unanticipated Problem Report whether the protocol and/or consent form(s) should be modified as the result of the UP. If the protocol and/or consent document(s) requires a revision, a modification must be submitted in Rascal.

#### **At the Time of Continuing Review of a Protocol:**

At the time of continuing review of a protocol, the Principal Investigator will submit a summary of all UPs that occurred during the review period and since the beginning of the study. The summary for each UP will include:

- The number of subjects who experienced the UP;
- The investigator's determination as to whether or not the UP was serious; and
- The investigator's determination as to the UP's relationship to the study procedures (e.g., definitely related, probably related or possibly related).

---

## 4 Statistical methods

### 4.1. Efficacy assessments

Specific Study Endpoints:

1. Percentage of patients with suppression of POMC level.
2. Percent change from Baseline of POMC level at each visit.
3. Percent change from Baseline of POMC level at final visit.
4. Percent change from baseline in pituitary tumor volume.
5. Change from baseline of fasting insulin or glucose levels or insulin sensitivity indices.
6. Change in HbA1C level

The primary outcome will be differences in POMC from baseline to 12 months after Pasireotide LAR therapy. We will also assess differences in POMC/ACTH ratios from pre to post-treatment. Changes in pituitary tumor size from pre to post-pasireotide therapy will be assessed. Patient characteristics will be summarized by descriptive statistics. Frequencies and percentages for categorical variables and mean, standard deviation, median, minimum and maximum for continuous variables. The paired t-test and Wilcoxon signed test will be used to evaluate the change in POMC level from baseline to final study visit as appropriate. Peptide levels and ratios will be compared by nonparametric approach. Repeated measures ANOVA will also be used to analyze the change in POMC levels over time during pasireotide therapy. Statistical Analysis will be performed by SAS 9.3.

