#### Interruption or discontinuation of treatment

Patients who experience an enlargement of their pituitary tumor or any clinical signs consider to represent progression of the tumor while on Pasireotide LAR therapy will be withdrawn from the study by the investigator. Patients that experience severe or life-threatening hyperglycemia (diabetic ketoacidosis, hyperosmolar coma), develop jaundice, hepatitis or other primary hepatic dysfunction will be discontinued from the study. Patients who develop an allergic reaction to Pasireotide LAR® Depot will be discontinued. It will be documented whether or not each patient completed the clinical study. If for any patient either study treatment or observations were discontinued the reason will be recorded. Reasons that a patient may discontinue participation in a clinical study are considered to constitute one of the following:

1. adverse event(s)
2. abnormal laboratory value(s)
3. abnormal test procedure result(s)

4. subject's condition no longer requires study treatment
5. protocol violation
6. subject withdrew consent
7. lost to follow-up
8. administrative problems
9. death

Any patient who receives at least one dose of trial medication will be included in the safety analysis.

	V1	V2	V3	V4	V5	V6	V7	V8	V9	V10	V11	V12	V13	V14	V15
OGTT (75 gm)		X					X							X	
CBC (w/ WBC differential)	X			X			X			X				X	
Hepatic Function Panel (AST, ALT, Bilirubins, AlkPhos)	X			X			X			X				X	
Basic Metabolic Panel (Na, K, Cl, HCO 3 , BUN, Cr, Ca)	X			X			X			X				X	
Serum Cortisol	X	X	X	X	X	X	X	X	X	X	X	X	X	X	
Plasma POMC	X	X	X	X	X	X	X	X	X	X	X	X	X	X	
Plasma ACTH	X	X	X	X	X	X	X	X	X	X	X	X	X	X	
Thyroid Panel (Free T4, TSH)	X														
Coagulation (PT, PTT)	X						X							X	
Serum & Plasma Bank	X	X	X	X	X	X	X	X	X	X	X	X	X	X	
Urinalysis	X							X						X	
Urine Pregnancy	X														
24 Hr Urinary Free Cortisol and Creatinine	X														
Salivary Cortisol (late night)(x5)	X							X						X	
Pituitary MRI w/ contrast	X							X						X	
Gallbladder Ultrasound and reading	X													X	
12 Lead ECG and reading	X	X	X	X			X			X				X	

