#### Adverse events

Information about all adverse events, whether volunteered by the subject, discovered by investigator questioning, or detected through physical examination, laboratory test or other means, will be collected and recorded in study-specific source documents and followed as appropriate. An adverse event is any undesirable sign, symptom or medical condition occurring after starting study drug (or therapy) even if the event is not considered to be related to study drug (or therapy). Study drug (or therapy) includes the drug (or therapy) under evaluation, and any reference or placebo drug (or therapy) given during any phase of the trial.

Medical conditions/diseases present before starting study treatment are only considered adverse events if they worsen or become more frequent after starting study treatment. Adverse events occurring before starting study treatment but after signing the informed consent form will be recorded in the subject records. Abnormal laboratory values or test results constitute adverse events only if they induce clinical signs or symptoms or require therapy, and will be recorded in study-specific Adverse Events source documents.

As far as possible, each adverse event will also be described by:

1. its duration (start and end dates),
2. the severity grade (mild, moderate, severe)
3. its relationship to the study drug (suspected / not suspected),
4. the action(s) taken and, as relevant, the outcome.

Guidelines for treatment of patients experiencing AEs (Per CTCAE V4.03)

Medication	Adverse event	Action
Pasireotide LAR i.m.	AE CTC grade $\leq$ 2	No drug adjustments

Medication	Adverse event	Action

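### Endpoints 5 and 6 measure glucose, insulin and HbA1c, which the protocol itself treats, but no stated analysis uses the antidiabetic-drug records

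*Combined protocol and SAP*

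**What the plan says.** Among the endpoints in section 4.1, number 5 is "Change from baseline of fasting insulin or glucose levels or insulin sensitivity indices" and number 6 is "Change in HbA1C level". Neither mentions antidiabetic drugs.

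The Hyperglycemia part of section 3.4.2 acts on the same variables. Intervention is to be implemented "in any patient meeting any of the following criteria: FPG > 130mg/dL or HbA1c" of at least 6.5%. A lower trigger applies to home fasting readings: "If any values are observed above 100mg/dL", guideline-based management follows, "aiming at a glycemic treatment goal of FPG < 130mg/dL". The text adds: "Appropriate actions such as initiation of anti-hyperglycemic therapy (and referral to diabetes specialist) will be taken by the investigator".

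Section 3.3.1 names metformin, sitagliptin and subcutaneous insulin as the expected, but not prescribed, order. Section 3.3.2 foresees dose adjustment in patients already on insulin or oral agents and has all antidiabetic drugs listed in source documents. Exclusion criterion 3 (section 3.2.1) allows diabetic patients to enter with HbA1c up to 8%.

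On the safety side, section 3.4.2 states: "Abnormal laboratory values or test results constitute adverse events only if they induce clinical signs or symptoms or require therapy". The text on interruption or discontinuation of treatment adds: "Any patient who receives at least one dose of trial medication will be included in the safety analysis".

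**The concern.** The patients whose glucose rises most are those most likely to receive a drug that lowers it before the next measurement. Endpoints 5 and 6 then record the joint result of pasireotide and diabetes treatment. A small mean change in HbA1c could coexist with several patients who needed new or more treatment, and these endpoints alone would not show it.

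This matters because section 1.2.1.1.1 gives hyperglycemia as the exception to an otherwise class-typical safety profile. For insulin the problem is different: a fasting value taken on injected insulin, or an index built on it, would be analysed as if it described the patient's own physiology.

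**Working it through.** **The plan's own figure.** The plan gives no figure for endpoints 5 and 6. Its only power statement (section 4.2) concerns POMC: a 20% fall, SD 15%, ten pairs, two-sided 0.05. The noncentrality is (20/15) × √10 = 4.22 on 9 degrees of freedom, which gives power of 96.2%. This agrees with the stated value above 90%, and nothing below depends on it.

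**1. Trigger against endpoint.** Fasting glucose is in endpoint 5 and triggers intervention above 130 mg/dL on FPG, or guideline action above 100 mg/dL at home. HbA1c is endpoint 6 and triggers intervention at 6.5%. The treatment goal for FPG equals its intervention threshold, so successful treatment brings the endpoint variable back below the value that prompted it.

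**2. Direction.** Let u be a patient's change in HbA1c (or glucose) without antidiabetic treatment and d > 0 the amount that treatment removes. The observed change is u − d.
- It is always below u, so the rise attributable to pasireotide is understated by d.
- If d < u, the change moves toward zero. If d > u, it passes below zero. Illustration with assumed values: entry 7.5%, u = 1.0, d = 1.5 gives 7.5 + 1.0 − 1.5 = 7.0, a change of −0.5.
- Fasting insulin and indices built on it have no fixed direction.

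**3. How many patients.** The documents give no rate of drug starts. As a proxy, take the acromegaly adverse-reaction rates in section 1.2.1.1.1, with X binomial, n = 10, and P(X ≥ 2) = 1 − (1−p)^10 − 10p(1−p)^9.

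| Proxy | p | 10p | P(X ≥ 1) | P(X ≥ 2) |
|---|---|---|---|---|
| Hyperglycemia, C2402, 40 mg | 0.333 | 3.33 | 0.983 | 0.896 |
| Hyperglycemia, C2305 | 0.281 | 2.81 | 0.963 | 0.819 |
| Diabetes mellitus, C2305 | 0.197 | 1.97 | 0.889 | 0.615 |
| Diabetes mellitus, C2402, 40 mg | 0.190 | 1.90 | 0.878 | 0.593 |

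Two to four affected patients is therefore a reasonable range to examine.

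**4. Shift of the ten-patient mean.** With k patients treated, the shift is (k/10) × d. Assume d = 0.5 to 1.5 HbA1c points; the documents give no value.
- k = 2: 0.10 to 0.30
- k = 3: 0.15 to 0.45
- k = 4: 0.20 to 0.60

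Example: three patients with u = 2.0 and d = 1.0, the others unchanged. The mean is 3 × 2.0/10 = 0.60 untreated and 3 × 1.0/10 = 0.30 treated. The rise is halved but still visible.

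**5. Precision of a patient count.** Exact (Clopper-Pearson) 95% intervals: 0 of 10, 0-30.8%; 2 of 10, 2.5-55.6%; 3 of 10, 6.7-65.2%; 4 of 10, 12.2-73.8%.

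**The case against.** The strongest reply is that an unqualified change from baseline is naturally read as change regardless of other treatment. That is a legitimate quantity: what happens to glycemia on pasireotide plus usual diabetes care. This stands, and the fix keeps it. What remains is that the plan does not say so and reports nothing beside it that would let a reader interpret it.

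Four stronger readings are tempting, and the documents do not support them.
- *The trial would lose sight of hyperglycemia.* It would not. A laboratory abnormality that requires therapy is an adverse event, recorded with the action taken, and every dosed patient enters the safety analysis. Only a patient who crosses a threshold without symptoms and without therapy might go uncounted there, and that patient's own change is not attenuated.
- *No summary or test applies to these endpoints.* Section 4.1 has a nonparametric provision for peptide levels, which may cover insulin. It also has a sentence on mean, SD, median and range for continuous variables. The scope of both is arguable, but their existence rules out the absolute claim. It also rules out an argument that a median would hide the rise, since no median-only summary is planned.
- *The bias is always toward no effect.* Step 2 shows that it can pass zero, notably in patients entering at HbA1c 6.5-8%.
- *Fasting samples are unscheduled.* The part of the visit schedule present in the text reviewed shows a 75 g OGTT at V2, V7 and V14. This is the likely source of fasting values, and other rows are missing from that text.

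It is also fair that insulin comes last in the expected order, so few patients may have insulin measures affected.

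**Conclusion.** The point holds as a minor one. Endpoints 5 and 6 are changed by treatment that the same variables trigger, and no stated analysis uses the drug records. In patients treated on study, the glucose and HbA1c changes understate the rise attributable to pasireotide. Insulin measures taken on injected insulin should not be read as the patient's own secretion or sensitivity.

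The size is not established. The 0.10 to 0.60 point range rests on an assumed effect of 0.5 to 1.5 points and on two to four treated patients. That number is taken from acromegaly adverse-reaction rates, which are not drug-start rates and come from another population.

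The two endpoints belong to no stated objective and are not in the power calculation. A reader might infer that the efficacy conclusion is at risk, but the primary POMC comparison does not use these variables.

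**What to change.** Add to section 4.1:

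(a) Keep the all-patient change from baseline and label it as regardless of antidiabetic treatment.

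(b) Beside it, report how many of the ten patients newly reach FPG above 130 mg/dL or HbA1c of at least 6.5% on laboratory values, or start or increase antidiabetic therapy. Show each component and an exact 95% interval. A patient above a threshold at baseline counts on that measure only through a start or increase. The start-or-increase component also catches patients treated on home readings.

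(c) Exclude fasting insulin and insulin-based indices for values taken on injected insulin, and state how many are excluded.

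(d) As a sensitivity analysis, show glucose and HbA1c change using only values before the first antidiabetic start or increase. Note that this cuts short the follow-up of the patients most affected.

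Items (b) and (c) matter most, because they change what the endpoints can show. The thresholds are the protocol's own and are used only for counting; no change in patient management is implied.

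The cost is a short paragraph, one table and one sensitivity analysis. The drug records and laboratory glucose are already planned. The downsides are a wide interval with ten patients, overlap with the adverse-event tables, a count that partly reflects prescribing habits, and selective loss from the insulin indices, possibly of the strongest glycemic responders.

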#### 1.2.1.1 Clinical Experience

##### 1.2.1.1.1 Pasireotide LAR

Pasireotide LAR has been extensively investigated in the clinical development program for healthy volunteers and various patient populations. Completed studies and studies with completed interim analyses are shown in the INVESTIGATOR'S BROCHURE, V15, P. 44, Table 5-1.

Pasireotide LAR demonstrated favorable PK profile for extended release in healthy volunteers and patients. PK steady state was achieved following 3 monthly (q28d) intra-muscular (i.m.) injections of pasireotide LAR in a study with both acromegaly and carcinoid patients. PK exposures of trough concentrations were approximately dose-proportional. CL/F of the Pasireotide LAR formulation was comparable to CL/F of the s.c. formulation (4.3-9.0 L/h). T1/2 for the Pasireotide LAR formulation was approximately 16 days, suitable for monthly dosing. The relative bioavailability of the Pasireotide LAR formulation to the s.c. formulation was complete, ranging from 106% to 148%. PK exposures in acromegaly patients were comparable to those in healthy volunteers. PK exposures in carcinoid patients were 2-fold higher than in healthy volunteers.

The efficacy of pasireotide LAR in acromegaly patients is based on CSOM230C2305, the phase III study to assess the safety and efficacy of pasireotide LAR vs octreotide LAR in patients with active acromegaly. In this study, pasireotide LAR was shown to be significantly superior to octreotide LAR for the treatment of acromegaly in medically naïve patients in terms of biochemical control (GH < 2.5 µg/L and normalization of IGF-1 levels) (31.3% vs. 19.2%; p-value 0.007), providing higher response rate in both de novo patients and in patients with prior pituitary surgery (25.7% vs. 17.3% in de novo patients; 39.4% vs. 21.8% in postsurgical patients). Pasireotide LAR was as effective as octreotide LAR in reducing tumor volume, improving acromegaly symptoms and ring size, and quality of life (27).

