In our ongoing "Prospective Study of Clinically Nonfunctioning Pituitary tumors" funded by the NIH (DK073040), we are prospectively studying a large cohort (currently 285) of patients who have presented with apparent clinically nonfunctioning pituitary tumors. One AIM of this study has been to identify silent corticotroph pituitary tumors based on measurement of plasma POMC levels. All patients have been screened with POMC measurements and POMC levels have been followed over time in patients who had elevated levels, in many also after surgical removal of the pituitary tumor. A number of patients in this cohort have been identified with levels of POMC above our normal range. Those patients with elevated plasma POMC levels were found to have pituitary tumors positive for ACTH on immunohistochemical analysis. We have also examined another group of patients with known silent corticotroph pituitary tumors and some of these patients have been found to have elevated plasma POMC levels. We hypothesize based on the rationale described above that these patients with clinically silent corticotroph pituitary tumors (ACTH positive on pathology) and elevated POMC levels in plasma will respond to pasireotide therapy. Detection of a lowering of the increased plasma levels of POMC by pasireotide would show that POMC measurement is a clinically relevant marker to follow during pasireotide treatment of silent corticotroph tumors. POMC levels could also

serve as a marker that identifies patients in whom pasireotide would be more likely to be effective. Although we do not have evidence yet that pasireotide will produce shrinkage of silent corticotroph tumors, POMC lowering may be associated with tumor shrinkage since somatostatin analog therapy typically produces tumor shrinkage when the biomarker of the tumor is suppressed reflecting tumor cell suppression. This will be tested in this study by examining tumor size changes along that of POMC levels in patients with silent corticotroph tumors.

Thus, our preliminary results suggest that plasma POMC levels will be a useful marker for silent corticotroph pituitary tumors. In this project, we will examine the use of plasma POMC level as a marker for the effectiveness of medical treatment of silent corticotroph tumors with Pasireotide.

[figure not shown]

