### 3 INVESTIGATIONAL PLAN

#### 3.1. Overall study design

This is an open-label, 12-month pilot study of Pasireotide LAR therapy of 10 patients with silent corticotroph pituitary tumors.

Pasireotide LAR 40 mg will be administered monthly. Baseline and monthly visits on therapy will monitor plasma levels of POMC, other pituitary function, safety labs, glucose tolerance, physical examination, and visual fields. Pituitary MRI will be done at baseline, 6 months and 12 months of therapy.

The starting dose is Pasireotide LAR 40 mg/month IM, this will be increased to 60 mg/month at 6 months if a fall in POMC levels and/or tumor shrinkage are not attained. LAR will be administered monthly with the last injection at Week 44.

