### 3.3. Treatment

#### 3.3.1. Investigational Therapy

Patients who have provided written informed consent will undergo screening procedures. Once eligibility is established patients will begin therapy with Pasireotide LAR 40 mg.

Pasireotide LAR 40 mg will be administered as intra-muscular (i.m.) intragluteal injections every 4 weeks. Uptitration will occur to Pasireotide LAR 60 mg after 6 months of therapy with Pasireotide LAR 40 mg if POMC level has not been suppressed and/or pituitary tumor shrinkage has not occurred. For patient receiving 40 mg dose down-titration to 20 mg is permitted for patients who do not tolerate 40 mg. For patients who are up-titrated to the 60 mg dose down-titration to 40 mg is permitted if tolerability issues occur on this higher dose.

Medication labels will comply with legal requirements and be printed in English. The storage conditions for study drug will be described on the medication label.

Should anti-diabetic treatment be needed during the study (see adverse events) this will be provided by the investigator according to standard clinical practice for diabetes care. The order of initiation of anti-diabetic therapy is expected to be, but is not prescribed as part of this protocol:

- Metformin at individual doses starting from 1000 mg/day to maximum dose according to the approved package insert and depending on the patient tolerability
- Sitagliptin 50 or 100 mg administered orally once a day

- Insulin administered s.c. according to package insert

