#### POMC Precursor ELISA:

POMC precursor will be performed by ELISA with antibodies provided by [name]. For this assay capture monoclonal antibody is directed against ACTH 10-18 and detection antibody is directed against  $\gamma$ -MSH. Affinity purified human 31K POMC is used for standards. The assay has 100% crossreactivity with 22K pro-ACTH but none with ACTH,  $\alpha$ -MSH or  $\gamma$ -MSH (16,29,30). Assay sensitivity is 7.5 fmol/ml. Normal values for this POMC precursor have been preliminary established by our group (14) and a large-scale normal value study for plasma POMC levels is currently being conducted by [name]. ACTH will be measured by solid phase, two-site sequential chemiluminescent immunometric assay and cortisol by solid-phase, competitive chemiluminescent enzyme immunoassay (Immulite 1000), UFC by Liquid-Chromotography-Tandem Mass Spectrometry and Late night salivary cortisol by Mass Spectrometry. Insulin will be measured by immunofluorometric assay (DPC Immulite). Glucose will be determined by automatic hexokinase method.

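### The supportive repeated measures ANOVA of POMC could lose patients with any missed visit or early withdrawal; a mixed model on all observed visits is a cheap improvement

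*Combined protocol and SAP*

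**What the plan says.** Section 4.1 tests the change in POMC from baseline to the final visit with a paired t-test or Wilcoxon test. It then adds: "Repeated measures ANOVA will also be used to analyze the change in POMC levels over time during pasireotide therapy". Its second listed endpoint is "Percent change from Baseline of POMC level at each visit". SAS 9.3 is named, but no procedure. There is no covariance structure, sphericity correction, missed-visit rule or efficacy analysis set. The only analysis set defined, in Section 3.3.2, is for safety.

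The visit table marks POMC at V1 to V14 and MRI at V1, V8 and V14. Section 3.1 says "Pituitary MRI will be done at baseline, 6 months and 12 months of therapy". If V8 is month 6 and V14 is month 12, V2 is month 0, which gives baseline plus 12 monthly values (V3 to V14).

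Section 3.3.2 (Interruption or discontinuation of treatment) requires that patients with tumor enlargement or clinical signs of "progression of the tumor while on Pasireotide LAR therapy will be withdrawn from the study by the investigator". Section 2.1 expects that "POMC lowering may be associated with tumor shrinkage".

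**The concern.** A classical repeated measures ANOVA needs a value at every visit from every patient. With 13 time points, one missed visit removes the whole patient, and so does withdrawal at the month-6 MRI. If POMC and tumor size move together, as Section 2.1 expects, patients withdrawn for enlargement are those least likely to show a fall in POMC. A complete-case time course would leave them out and look too favourable.

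There is also an error-rate issue. Monthly values in one patient are likely to correlate more strongly when close together, which breaks sphericity and makes the uncorrected F test reject too often. The multivariate alternative cannot be computed: it needs 12 contrasts, and 10 patients give 9 degrees of freedom.

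What is at stake is the supportive description of POMC over time. The primary test is a separate analysis.

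**Working it through.** **Inputs from the documents.** 10 patients (Section 3.2); 12 post-baseline POMC visits (visit table, with V2 as month 0); 20% fall, SD of change 15%, two-sided 0.05, 10 pairs, power above 90% (Section 4.2).

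**Assumptions.** Miss rates, clustering of misses, number of withdrawals, correlation structures and response profiles. The documents give none of these as inputs.

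**1. The plan's own figure.** Paired t-test, noncentrality (20/15) × √10 = 4.216, 9 df, critical t 2.262: power 96.2%. This agrees with the stated figure. With 8 pairs the noncentrality is (20/15) × √8 = 3.771, 7 df, critical t 2.365: power 89.6%.

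**2. Patients left in a complete-case ANOVA.** With independent misses at rate p, the expected number is 10 × (1 − p)^12. Clustered misses use a beta-binomial with intraclass correlation 0.2.

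| Miss rate p | Independent | Clustered |
|---|---|---|
| 2% | 10 × 0.785 = 7.8 | 8.9 |
| 5% | 10 × 0.540 = 5.4 | 7.4 |
| 10% | 10 × 0.282 = 2.8 | 5.4 |

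With 5% independent misses and 2 withdrawals after V8: 8 × 0.540 = 4.3.

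**3. Type I error of the overall visit test** (simulation, 10 complete patients, 13 time points, AR(1) correlation, nominal 5%). Uncorrected F: about 6% at correlation 0.3, 8% at 0.5, 11% at 0.7 and 14% at 0.9. Huynh-Feldt: 5.3-6.7%. Greenhouse-Geisser: about 1-4%. The mixed model proposed below, with 5% of visits missed, with or without the 2 withdrawals: 2-7%.

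**4. Power of the overall visit test** (20-point fall, change SD 15; ranges are over the assumed covariance structures).

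| Profile and missing data | Complete-case Huynh-Feldt | Mixed model |
|---|---|---|
| Fall reached by month 3, none missed | 98-100% | 97-100% |
| Fall reached by month 3, 5% missed | 73-91% | 96-100% |
| Steady fall over 12 months, none missed | 95-100% | 70-100% |
| Steady fall over 12 months, 5% missed | 72-93% | 71-100% |

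The month-3 profile follows the statement in Section 1.2.1.1.1 that "PK steady state was achieved following 3 monthly (q28d) intra-muscular (i.m.) injections of pasireotide LAR". A separate set of runs gave Huynh-Feldt power falling from about 95-99% with no missed visit to 67-75% with 5% missed.

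**5. Selection.** Suppose 2 withdrawn patients have no fall and the other 8 fall by 20 points. The true mean is (8 × 20 + 2 × 0)/10 = 16. Complete cases show about 19-21. The mixed model shows 16.6-19.5 across two sets of runs. It removes part of the bias only.

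**6. Single-visit tests in the mixed model.** Type I error is 3-6% when the covariance form is right. It is 11-18% if patients truly differ in response (50-64% of the change variance). The paired t-test stays at 4.1-6.5%.

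**The case against.** The strongest reply is that the loss stacks two assumptions. The plan does not say the ANOVA is complete-case, and SAS could fit repeated measures as a mixed model. Independent misses are also not an obvious base case, because most POMC visits fall at about the time of an injection. Both points stand. A reader might infer that the plan will discard about half of its patients; the documents do not support that. Visit windows or make-up rules may also stand in parts of the visit schedule that cannot be read in the available text.

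A reader might also infer that the ANOVA is the only POMC analysis over time. That goes too far: the sentence before it promises a nonparametric comparison of peptide values and their ratios. It is vague, but it could cover visit-by-visit comparisons.

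Third, the selection problem is not peculiar to the ANOVA. Withdrawn patients with no final value would drop out of the primary paired test too. This stands, so the sensitivity analysis should cover both.

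Finally, the mixed model has its own weaknesses. Section 3.3.1 foresees non-response ("if POMC level has not been suppressed and/or pituitary tumor shrinkage has not occurred"), and that is the setting in which its single-visit tests are anti-conservative. With no missed visits it has no advantage, and for a steady fall its power can be lower (70% against at least 95%). These limits stand. They argue for paired intervals beside the model, not for leaving the ANOVA sentence as it is.

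**Conclusion.** The concern holds as a minor point. The plan names a method that, in its classical form, suits 13 time points in 10 patients poorly. It also leaves open a correction that moves the type I error between about 1% and 14%. How many patients would be lost depends on assumed miss rates and on a complete-case run: 2.8 to 8.9 of 10 remain over the range shown.

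Two stronger readings should be avoided. The mixed model does not cure the selection caused by progression withdrawals; it reduces it. Nor does this point overturn the stated power: intermittent misses leave the 96.2% untouched. Missing final values are a different matter, since 8 pairs give 89.6%, just under the plan's stated level. The documents do not say how many to expect.

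**What to change.** Replace the ANOVA sentence in Section 4.1 with:

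> As a supportive analysis, ln(POMC) at all observed visits from baseline onward will be analysed by a linear mixed model (REML; visit as a categorical effect, random patient intercept, AR(1) residuals, Kenward-Roger df), with the number of patients contributing at each visit; paired t intervals for change from baseline will be shown beside the model estimates. As a sensitivity analysis, patients withdrawn for progression will be given their baseline value at later visits, in this model and in the baseline-to-final paired comparison.

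State whether V1 or V2 is the baseline. To show what the sensitivity rule does: if 8 patients have a ratio of 0.80 and 2 are set to no change, the mean ratio becomes 0.80^0.8 = 0.837.

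If the ANOVA is kept, apply the Huynh-Feldt correction and report how many patients enter it. That controls the error rate but does not bring back lost patients.

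**Cost.** A few lines of text and a little more work in the SAS already named; no new data. The model assumes a covariance form and data missing at random. The log scale needs a convention for values under the assay limit ("Assay sensitivity is 7.5 fmol/ml"): one such value among 10 patients moves that visit's ratio by 1 − (5.3/7.5)^(1/10) = 3.4% between substituting 5.3 and 7.5.
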